The primary objective of this project, which reflects specific aim 2 of Drs. [name]/[name]'s AHA grant, is therefore to identify high risk, sedentary, middle aged obese individuals with high visceral fat levels, and initiate an exercise program in conjunction with omega-3 fatty acid supplementation designed to reduce visceral adiposity and regress myocardial triglyceride accumulation. Findings from this aim would have enormous public health significance and establish a novel, practical exercise training program and “nutri-ceutical” strategy to reverse obesity related cardiovascular remodeling.

Hypothesis:

High aerobic exercise training in conjunction with daily omega-3 supplementation will reduce visceral myocardial triglyceride accumulation by reducing visceral adiposity. A reduction of myocardial fat will lead to improved LV structure and diastolic function by an approach that is not necessarily predicated on weight loss.

Specific Aim:

To test our hypothesis that reduction in myocardial triglyceride content will improve markers of

diastolic function, we have designed a randomized, double blind, placebo controlled trial. We will study four groups of previously sedentary obese middle aged subjects at high risk for development of HF for one year with the following interventions: A) sedentary controls taking placebo; B) sedentary subjects taking omega-3 fatty acids; C) subjects undergoing high intensity aerobic exercise training while on placebo and D) subjects undergoing high intensity aerobic exercise training while taking omega-3 fatty acids. Subjects will be categorized as high risk and enrolled on the basis of elevated serum biomarkers (cTnT) and high visceral fat content (>2.5 kg). We will perform comprehensive non-invasive assessments of cardiovascular structure and systolic/diastolic function before and after 1 year of an exercise intervention involving high intensity intervals and omega-3 administration. We anticipate the combination of high intensity aerobic exercise in conjunction with high dose omega-3 supplementation will reduce visceral adiposity, decrease myocardial triglyceride content and improve markers of diastolic and vascular function.

Background:

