To test the hypothesis that 1 year of exercise training in conjunction with daily oral administration of omega-3 poly-unsaturated fatty acids in obese individuals at high risk for developing HF will regress myocardial triglyceride content and improve cardiac function, we have designed a randomized, double blind, placebo controlled trial. We will study four groups of previously sedentary obese middle aged subjects for one year with the following interventions: A) sedentary controls taking placebo; B) sedentary subjects taking omega-3 fatty acids; C) subjects undergoing high intensity aerobic exercise training while on placebo and D) subjects undergoing high intensity aerobic exercise training while taking omega-3 fatty acids. We will perform comprehensive non-invasive assessments of cardiovascular structure and function in all groups before and after 1 year of training.

Subject Population:

Subjects for this specific aim will be recruited from the Dallas Heart Study (DHS), a population based, probability sample of 6,101 individuals in the Dallas community, used by the PI in the previous studies. Approximately 250 individuals meet inclusion criteria for our study and have 1) ejection fraction >0.50 ; 2) >2.5 kg visceral fat (intra- and retro-peritoneal adipose tissue) documented by MRI; 3) either a positive high sensitivity troponin, or NTBNP in the 4th quartile of the DHS; 4) age range 40 -60 and 5) BMI range 30 – 50. All these subjects will be sent a letter followed up by a telephone call as we have done previously. Interested volunteers will be invited to the laboratory for consent, screening and familiarization. The advantages of this population include: a) the presence of a multi-ethnic sample oversampled for African-Americans, assuring a high likelihood for inclusion of sufficient ethnic minorities; b) recruitment from a database including individuals already favorably disposed to and experienced in cardiovascular research; c) clear documentation that all volunteers approached for the study are at high risk for the development of HFpEF; d) the use of a probability based design assuring a representative sample of the individuals in the appropriate age ranges free of biases associated with self-selected volunteers. This approach facilitates making inferences from the data at the population level

(high external validity).

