To test the hypothesis that reduction in myocardial triglyceride content will improve markers of diastolic function, we have designed a randomized, double blind, placebo controlled trial. To recap, we will study four groups of previously sedentary obese middle aged subjects at high risk for development of HF for one year with the following interventions: A) sedentary controls taking placebo; B) sedentary subjects taking omega-3 fatty acids; C) subjects undergoing high intensity aerobic exercise training while on placebo and D) subjects undergoing high intensity aerobic exercise training while taking omega-3 fatty acids. We anticipate the combination of high intensity aerobic exercise in conjunction with high dose omega-3 supplementation will reduce visceral adiposity, decrease myocardial triglyceride content and improve markers of diastolic and vascular function.

We will need to complete baseline testing on 80 subjects to enter the 1 year intervention with 44 assigned to exercise and 36 to yoga control. This difference is designed to account for differences in compliance within the 2 exercise groups. Within each exercise/yoga group, half of subjects will be randomized to placebo or omega-3 fatty acid supplementation. For the exercisers, 22 subjects will be given placebo and 22 will be given omega-3. For the yoga control, 18 will receive placebo and 18 will receive omega-3. Ultimately the study is powered to end up with 15 subjects per group (total N=60) accounting for drop outs to complete all follow up testing (please see “power calculations” section on page 697 (of 731) of the AHA grant, submitted as “protocol” which develops and supports these numbers in some detail).

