As this study is sponsored by the AHA and passed peer review, the biostatistics section is omitted per instructions, but is available in the full protocol. (page 697 of 731 of the AHA grant). Briefly, the primary outcome of interest is reduction in myocardial triglyceride content by MRI spectroscopy. Secondary outcome measures are LV concentric remodeling and diastolic function. The sample size for the study was calculated using a two factor factorial design which provides adequate power to detect a main effect (99%) as well multiple comparisons between individual groups (80%).

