**NCT number: NCT03448185**

**Document date: 1/6/2014**

## Power Calculations

Per protocol analysis will be performed and include only subjects who have completed at least 80% of the prescribed training. The primary outcome for this aim will be reduction in cardiac lipid content after intervention targeting visceral fat. Myocardial triglyceride content in obese subjects with metabolic syndrome is approximately 0.9% with a standard deviation of 0.4%. We anticipate a reduction of approximately 50% to 0.45% based on prior studies. In a 2x2 design with subjects randomized to HIIT or yoga and O3-PUFA or placebo, 60 subjects will need to be enrolled to detect an absolute reduction in mean TG content to 0.45% (from 0.9%) with a standard deviation of 0.4%, alpha of 0.05 and power of 80%. To analyze the cardiac effects of reducing visceral adiposity between groups, a mixed model repeated measures analysis will be used for continuous variables such as LV mass index, LV concentricity index, and diastolic strain adjusting for age, sex and hypertension. Descriptive statistics will be used to characterize changes in anthropomorphic parameters (e.g. BMI, lean body mass) and serum biomarkers (cTnT, NT-proBNP) using a 3 factor (time, exercise, drug) repeated measures analysis of variance between the four groups.

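### Are the stated 99% and 80% power in doubt because the plan does not say which contrast the 0.45-point fall describes?

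*Protocol*

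**What the plan says.** The Protocol's Biostatistics section is a short summary that refers the reader to a page of the grant. It says "The sample size for the study was calculated using a two factor factorial design" and claims "adequate power to detect a main effect (99%) as well multiple comparisons between individual groups (80" (99% for a main effect, 80% for group comparisons). The Study design section fixes the evaluable number: "Ultimately the study is powered to end up with 15 subjects per group (total N=60", and cites the same grant page for the detail.

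The SAP's Power Calculations section supplies the inputs. The outcome is described as follows: "The primary outcome for this aim will be reduction in cardiac lipid content after intervention targeting visceral fat". The effect is "We anticipate a reduction of approximately 50% to 0.45% based on prior studies", from 0.9%. The remaining inputs are given as "with a standard deviation of 0.4%, alpha of 0.05 and power of 80" per cent, with 60 subjects in a 2x2 design.

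The Protocol's Hypothesis joins the two treatments: "High aerobic exercise training in conjunction with daily omega-3 supplementation will reduce visceral myocardial triglyceride accumulation by reducing visceral adiposity". Experimental Design and Methods does the same ("To test the hypothesis that 1 year of exercise training in conjunction with daily oral administration of omega-3 poly-unsaturated fatty acids"). The last paragraph of Background describes the primary objective as an exercise programme, and an earlier paragraph there presents omega-3 as a supplement to it.

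**The concern.** Two power figures are quoted for a factorial trial, but only one effect size is given, and it is attached to an unspecified intervention. In a 2x2 design the two main effects add up to the difference between the combined arm and control. So it matters whether 0.45 is one factor's main effect or the combined-against-control difference. Because the hypothesis is worded for exercise together with omega-3, the second reading is open. Under it, a 99% main effect for one factor leaves an average effect of about zero for the other.

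The 80% is also loosely described. It is said to cover multiple comparisons, but no number of comparisons, adjustment or sidedness is given. If the figures covered less than they seem to, a null omega-3 result, or a null result for the combination against exercise alone, could be read as strong evidence of no effect when the power had been modest.

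**Working it through.** **Inputs.** Difference 0.9 − 0.45 = 0.45 points, SD 0.4 and alpha 0.05 (SAP, Power Calculations); 15 evaluable per group, hence 30 against 30 for a main effect (Protocol, Study design). Assumptions: two-sided tests, equal completers per group, and SD 0.4 applying to the quantity analysed.

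**Formula.** Standard error = SD × √(2/n), with n per side. Power ≈ Φ(difference / standard error − z), where z is the two-sided critical value. The t figures use the noncentral t with 56 df (four-group error) or 28 df (two groups only).

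**Main effect (stated 99%).** Standard error = 0.4 × √(2/30) = 0.1033. 0.45 / 0.1033 = 4.357, and 4.357 − 1.960 = 2.397, so power is 99.2% (normal) or 99.0% (t). The stated figure reproduces.

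**Group comparisons (stated 80%).** Standard error = 0.4 × √(2/15) = 0.1461, and 0.45 / 0.1461 = 3.081.

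| Two-sided comparisons | z | Normal | t, 56 df | t, 28 df |
|---|---|---|---|---|
| One, unadjusted | 1.960 | 86.9% | 85.7% | 84.5% |
| Two, Bonferroni | 2.241 | 79.9% | 77.9% | 75.8% |
| Three, Bonferroni | 2.394 | 75.4% | 72.8% | 70.1% |
| Six, Bonferroni | 2.638 | 67.1% | 63.6% | 59.9% |

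As a floor, 80% is met by any single unadjusted pair. As an exact figure it matches two Bonferroni pairs by the normal formula: n = 2 × [0.4 × (2.241 + 0.842) / 0.45]² = 15.02 per group, in line with the plan's 15. That match is not unique, since three one-sided Bonferroni comparisons give 80 to 81% by t.

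**The alternative reading.** Let A be control, B omega-3, C exercise and D combined. The exercise main effect is (A + B − C − D)/2 and the omega-3 main effect is (A + C − B − D)/2. Their sum is A − D, with or without interaction. If A − D = 0.45:

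- 99% for one factor by t needs a main effect of 0.451, leaving about zero for the other.
- An equal split of 0.225 gives 0.225 / 0.1033 = 2.179, and 2.179 − 1.960 = 0.219, so 58.7% (normal) or 57.2% (t) for each factor.
- A 0.30 / 0.15 split gives 81% and 30% (t).

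So with both factors active to any real extent, this reading cannot produce the 99% that the Protocol states. Taking 0.45 as a single factor's main effect produces it directly.

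**The case for a change.** The best case for acting is that the text does leave the choice open. The Hypothesis and the Experimental Design and Methods section speak of the combination, and the SAP does not name the intervention. The 99% also cannot sensibly hold for both factors at once: two main effects of 0.45 would make the combined arm fall by 0.90, the whole of the 0.9% baseline. Yet a reader of the Biostatistics section might assume that it covers either factor. Two-sided Bonferroni adjustment for three or more pairs takes the power below 80%. Two sentences would settle all of this at no cost.

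Part of this stands. The documents do not name the factor, and they do not give the number or the adjustment of the comparisons. It does not follow that a figure is wrong. The Biostatistics section does name the type of contrast for the 99%, a main effect, and the only effect size in the documents reproduces it. Background supports exercise as the main factor, although the Objectives state the aim jointly. The adverse figures (57%, or a zero main effect) all need a contrast that no passage asserts. Even then, a zero main effect is an average over the other factor and would not rule out an effect at one of its levels.

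The risk of misreading a null result is also limited. Such a result is judged from its confidence interval, whose approximate half-width at the planning SD is 1.960 × 0.1033 = 0.20 points for a main effect and 1.960 × 0.1461 = 0.29 for a pair, whichever contrast the planners had in mind.

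**Conclusion.** The concern does not hold as a fault in the plan. On the documents' own inputs, the main-effect power is 99.0 to 99.2%. The pairwise power is 84 to 87% unadjusted and 76 to 80% for two Bonferroni pairs. It falls to 70 to 75% for three and 60 to 67% for six, but the plan commits to neither family. What is missing is a label: which factor carries the 0.45, and which comparisons the 80% covers. The Biostatistics section presents itself as a summary and refers to the grant page for the detail. That page, as cited, was not available to check, so it is not known whether it supplies the label.

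Supplying it would leave the 60 evaluable subjects, the 2x2 allocation and the analysis as they are. An analyst would take 0.45 as one factor's main effect, because that is what yields the stated power.

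The conclusion assumes two-sided tests, 15 completers in each group and SD 0.4 for the analysed quantity. A raw change score has that SD if baseline and follow-up correlate at 0.5; at zero correlation, main-effect power would be 86 to 87%. The documents give no correlation.

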**NCT number: NCT03448185**

**Document date: 1/6/2014**

## Power Calculations

Per protocol analysis will be performed and include only subjects who have completed at least 80% of the prescribed training. The primary outcome for this aim will be reduction in cardiac lipid content after intervention targeting visceral fat. Myocardial triglyceride content in obese subjects with metabolic syndrome is approximately 0.9% with a standard deviation of 0.4%. We anticipate a reduction of approximately 50% to 0.45% based on prior studies. In a 2x2 design with subjects randomized to HIIT or yoga and O3-PUFA or placebo, 60 subjects will need to be enrolled to detect an absolute reduction in mean TG content to 0.45% (from 0.9%) with a standard deviation of 0.4%, alpha of 0.05 and power of 80%. To analyze the cardiac effects of reducing visceral adiposity between groups, a mixed model repeated measures analysis will be used for continuous variables such as LV mass index, LV concentricity index, and diastolic strain adjusting for age, sex and hypertension. Descriptive statistics will be used to characterize changes in anthropomorphic parameters (e.g. BMI, lean body mass) and serum biomarkers (cTnT, NT-proBNP) using a 3 factor (time, exercise, drug) repeated measures analysis of variance between the four groups.

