However, not every subject who enrolls in the study will go onto complete testing. During testing, exclusion criteria may be identified requiring disqualification from the study; examples include the identification of coronary artery disease by cardiopulmonary stress testing. Furthermore, subjects may wish to withdraw from testing for personal or health related reasons. This requires “enrolling”, or consenting, a total of 120 subjects. We plan to enroll these 120 subjects over an 18-month period and will halt enrollment after 80 volunteers have completed all pre-testing as described above. Ideally, our protocol can be completed in 12-14 months; however, unexpected interruptions occasionally occur, extending the protocol up to as much as 24 months. With these delays taken into consideration, we expect to conclude our study in roughly 36 months (3 years). All enrollment and testing will be performed at our facility, making this a

single site study.

Following completion of the baseline studies, volunteers will be randomized to either an exercise intervention, or yoga/Tai Chi control. Subjects will be stratified by sex and allocated to the either exercise or yoga intervention using a stratified block randomization at a 1.2 to 1 exercise to yoga ratio (allowing for greater attrition for the exercise group). The randomization schema will be programmed using SAS Proc Plan and performed by [name], a biostatistician on our team. An active yoga/Tai Chi control allows for equipoise for the volunteers by improving quality of life without affecting fitness. It also controls for the contact with study staff; we are using this approach for the non-exercise controls in our current clinical trial (NCT02039154).

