For the exercise group, workouts may vary depending on subject preference (walk, cycle or rowing ergometer). For the first four weeks, subjects will perform low intensity exercise (~50-60% maximal predicted heart rate) for 20 – 30 minutes 3 – 4 times per week to familiarize themselves with equipment, operation of heart rate monitors and develop a habitual exercise schedule. After 4 weeks, subjects will then begin HIIT sessions once per week, increasing to twice weekly after 4 weeks. For HIIT sessions, subjects will warm up at light to moderate intensity for 10 minutes before starting interval exercise (90-95% of maximum HR or Borg scale of 17-18) for four minutes followed by an active recovery period (50-60% of maximum HR) of 4 minutes. Each interval session will comprise 4 cycles (interval/recovery) for a total exercise time of 32 minutes not including warm up. For the remaining 10 months (for a total exercise intervention duration of 12 months), subjects will be required to perform 2 HIIT sessions per week but encouraged to do 3 sessions if possible. Once they have started HIIT, subjects will not be required to continue with low intensity exercise sessions but may do so on their own accord. An experienced exercise physiologist will directly monitor the first few HIIT sessions. Subjects will work closely with their assigned physiologist and review heart rate monitor logs to ensure proper performance of HIIT.

For the yoga group, subjects will be encouraged to participate in yoga/tai chi/pilates classes at the Finley Ewing Cardiovascular Center at Texas Health Resources Dallas, or a gym/recreation center of their choice that is approved by one of the exercise physiologists on the research team. The goal for this group is exercise classes that will be of benefit to them, but that will not include sustained aerobic, endurance exercise. In place of a group exercise class, subjects will have the option of purchasing videos for home use. The subjects will be encouraged to participate in some form of non-endurance training at least 3 days per week. Each subject will receive an exercise log in which they will be expected to record their training.

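### The only analysis set stated is per-protocol (at least 80% of training), so the exercise v yoga contrast is selected after randomisation by a hurdle that differs between arms

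*SAP*

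**What the plan says.** The SAP (Power Calculations) defines the analysis set in one sentence: "Per protocol analysis will be performed and include only subjects who have completed at least 80% of the prescribed training". Neither document mentions an as-randomised or sensitivity set.

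The protocol (Study design) randomises after baseline testing and before training, 44 to exercise and 36 to yoga. Of the unequal split it says "This difference is designed to account for differences in compliance within the 2 exercise groups" and, of the 1.2 to 1 ratio, "allowing for greater attrition for the exercise group". The target is "15 subjects per group (total N=60) accounting for drop outs to complete all follow up testing".

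The training requirement is worded differently in the two arms:

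- **Exercise:** "subjects will be required to perform 2 HIIT sessions per week but encouraged to do 3 sessions if possible". Subjects and their physiologist "review heart rate monitor logs to ensure proper performance of HIIT".
- **Yoga:** "The subjects will be encouraged to participate in some form of non-endurance training at least 3 days per week". The record is the subject's own: "Each subject will receive an exercise log in which they will be expected to record their training".

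Within each training arm, subjects are randomised 1:1, double-blind, to omega-3 or placebo. The protocol's Biostatistics section quotes 99% power for a main effect and 80% for comparisons between individual groups, and refers to a grant page for detail.

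**The concern.** Randomisation makes the arms comparable as assigned. A rule based on a year of attendance replaces those arms with self-selected subsets. Subjects who sustain 80% of a year of HIIT may differ from those who do not in traits related to myocardial triglyceride, the primary outcome. If the two arms lose different proportions, or different kinds of subject, the contrast between the remainders mixes the training effect with that selection.

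Equal removal cannot be presumed here. The plan expects worse compliance with exercise. Eighty per cent of 2 required sessions is 1.6 a week. Eighty per cent of 3 encouraged days would be 2.4 a week, if encouragement counts as prescription at all, and the documents do not say whether it does.

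The same rule removes subjects from the blinded omega-3 contrast for missing training, which says nothing about whether they took their capsules.

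The documents do not say how many subjects the rule is expected to remove, or whether 15 per group is counted before or after it.

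**Working it through.** **Inputs from the documents.** Triglyceride 0.9% falling to 0.45% (difference 0.45 percentage points), SD 0.4, alpha 0.05 (SAP); 44 v 36 randomised, 15 per cell at the end (protocol). Two-sided tests are assumed.

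**The plan's own figure.** Main effect, 30 v 30: SE = 0.4 × √(2/30) = 0.103. Non-central t on 56 df gives power 99.0%, matching the stated 99%. A single-cell contrast, 15 v 15, gives 85.7% unadjusted, against 80% stated.

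**Implied losses.** Exercise (44 − 30)/44 = 31.8%; yoga (36 − 30)/36 = 16.7%. How these divide between drop-out and falling below 80% is not given.

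**Bias from the rule when there is no true effect.** If a fraction q of an arm is removed, and those removed differ from those kept by g, the kept mean is shifted by g × q. The bias is therefore g × (q_exercise − q_yoga). Both g (0.1 to 0.4, where 0.4 is a full SD) and the removals are assumptions.

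If 15 per group is counted before the rule, then q = x/30 and y/30, and df = number remaining − 4. If it is counted after the rule, then q = x/(30 + x) and y/(30 + y), with 30 v 30 remaining and 56 df.

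| Removed, exercise v yoga | Before: bias | Before: type I error | After: bias | After: type I error |
|---|---|---|---|---|
| 3 v 0 | 0.010 to 0.040 | 5.1% to 6.6% | 0.009 to 0.036 | 5.1% to 6.4% |
| 9 v 3 | 0.020 to 0.080 | 5.3% to 10.3% | 0.014 to 0.056 | 5.2% to 8.3% |
| 9 v 0 | 0.030 to 0.120 | 5.8% to 17.8% | 0.023 to 0.092 | 5.6% to 14.2% |

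In simulation (40,000 runs) the first set of error rates came out at 5.0% to 6.7%, 5.3% to 10.4% and 5.6% to 17.9%. The same subjects analysed as assigned gave 3.6% to 4.9%.

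**Charging all the implied loss to the rule.** 14/44 − 6/36 = 0.152. Bias is 0.015 to 0.061 and type I error 5.2% to 8.9% for g = 0.1 to 0.4.

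**Omega-3.** Removing an assumed 3 to 12 of 60 raises the variance by 60/57 − 1 = 5.3% to 60/48 − 1 = 25%. No power is given, because the SAP does not say which factor produces the 0.45 reduction.

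**Power if all are analysed as randomised.** Assume 0.45 is the exercise effect and that 14 of 44 exercisers keep a fraction k of it. With p = 30/44, the mean effect is 0.45 × (p + k(1 − p)) and the exercise-arm SD is √(0.16 + p(1 − p)(0.45(1 − k))²). For k = 0 these are 0.307 and 0.452; for k = 0.5, 0.378 and 0.413. The yoga SD stays at 0.4.

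| Measured | Contrast | Power, k = 0 to k = 0.5 |
|---|---|---|
| 80 | main effect, 44 v 36 | 89% to 98% |
| 80 | single cell, 22 v 18 | 61% to 83% |
| 60 | main effect, 30 v 30 | 78% to 94% |
| 60 | single cell, 15 v 15 | 49% to 71% |

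If instead only 3 (k = 0.5) to 9 (k = 0) of 30 measured exercisers fall below 80%, main-effect power is 98% to 80% and single-cell power 81% to 51%.

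**The case against.** - **Unseen text.** The protocol says the cited grant page supports its numbers in some detail, yet the SAP text contains neither the 44/36 split nor the 99%. There may be more text, and it may include an as-randomised analysis. This stands as a limit: the finding is that none is stated in the available documents. If one exists, it should be brought into the SAP.
- **One rule, not two.** The 80% threshold is nominally common to both arms, and the heart rate logs are described as a check on quality rather than on eligibility. That is fair as to how 80% will be scored, which is not stated. What is asked of each arm, and how it is recorded, still differs.
- **The upper figures are extreme.** The 17.8% needs 9 v 0 removals and a full-SD gap. Adjusting for baseline, or analysing change, would push the gap towards the low end, and linking the 44/36 split to compliance favours counting 15 per group after the rule. All of this stands, and the more moderate figures deserve more weight. Equal removal with equal gaps gives no bias.
- **The question is mechanistic.** An effect in adherers is a legitimate target, and the plan does call the analysis per-protocol. But the protocol also claims a practical public-health strategy, which needs the effect of assignment.
- **The remedy is imperfect.** There is no 6-month MRI, so a mixed model gains little for subjects without a 12-month triglyceride value. This stands as a cost.
- **Omega-3 is less exposed.** It is blinded, with the same hurdle for both capsules within each training arm. Agreed: the certain harm there is lost precision.

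**Conclusion.** The concern holds. In the available text the primary exercise contrast has no analysis that preserves randomisation, and its only analysis set is chosen on post-randomisation behaviour that the plan expects to differ by arm. The size and direction of any bias cannot be derived from the documents. Under the stated assumptions the type I error is near nominal (5.1% to 5.8%) for a gap of 0.1 and reaches 17.8% in the least favourable case. Drop-out before follow-up testing is a separate problem and is not counted in these figures. This should be fixed; it does not show that the trial would give a wrong answer.

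**What to change.** 1. Make the primary analysis all randomised subjects as assigned, and seek the already planned 12-month MRI whatever the training attendance.
2. Name myocardial triglyceride in the mixed model that the SAP already plans for other cardiac variables, or use multiple imputation with baseline triglyceride and the 6-month fitness and body composition data. Add a sensitivity analysis for departures from missing at random.
3. Keep the 80% set as a labelled adherer analysis, and define prescribed training in each arm.
4. Report by arm, separately, the losses to drop-out and to the 80% rule.
5. Exclude no one from the omega-3 contrast for missed training.
6. Restate the 99% and 80% power for the as-randomised analysis.

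The cost is SAP wording and the effort of bringing back subjects who stop training; the protocol already pays in proportion to procedures completed. The exercise effect is diluted. Main-effect power remains reasonable in most of the cases shown, but single-cell comparisons may fall well below 80%, and restating the power discloses that loss without curing it.
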